The Russian Multicenter Observational Program

Obtaining of data on the impact of different treatment modalities on the quality of life of the patients with acute and chronic hemorrhoid disease (EQUALISER)

PROTOCOL

NCT03743311

Protocol № IC4 -05682-058-RUS

Data of report: 1/03/2019

Introduction

Any long-term morbid condition associated severe physical discomfort, including hemorrhoids, is a powerful stress factor that affects psychological and physiological components of a person's health.

As of today, about 10% of adults in total population suffer from hemorrhoids, and this disease accounts for more than 40% of all cases of coloproctological diseases [1, 2, 3]. The prevalence of hemorrhoids is about 130-145 cases per 1,000 adult population, and in the group of middle-aged and elderly adults it reaches 210-240 cases per 1,000 population [2, 4].

The main method of treating chronic hemorrhoids of grade III-IV is surgical one [2, 3]. At the same time, the symptoms of hemorrhoids in grade 1-2 are successfully relieved with conservative treatment.

Criteria for assessing the treatment efficacy in acute and chronic hemorrhoids are the rates of complications and relapse of the major clinical manifestations of the disease. In addition to quantitative indicators of treatment efficacy, qualitative methods are becoming increasingly important, and one of them is an assessment of the quality of life (QoL) of patients [5, 7,6]. The purpose of this program is to obtain data on the effect of different treatment approaches in acute and chronic hemorrhoids in a broad cohort of patients in routine clinical practice.

References:

1. Благодарный Л.А. Как улучшить результаты хирургического лечения геморроя / Л.А. Благодарный, Ю.А. Шелыгин. // *Consilium Medicum. Хирургия.* – 2006. – № 1. – С. 49–52.
[Blagoradny L.A. How to improve the results of surgical treatment of hemorrhoids / Blagoradny L.A., Shelygin Yu.A. // *Consilium Medicum. Surgery.(Supplement).* - 2006. - No. 1. - P. 49-52. (in Russ.)]
2. Воробьев Г.И. Геморрой / Г.И. Воробьев, Ю.А. Шелыгин, Л.А. Благодарный. – М.: Литтерра, 2010. – 200 с.
[Vorobyev G.I. Hemorrhoids / Vorobiev G.I., Shelygin Yu.A., Blagoradny L.A.. - Moscow: Litterra, 2010. - 200 p. (in Russ.)]
3. Ривкин В.Л. Геморрой и другие заболевания заднепроходного канала / В.Л. Ривкин, Ю.В. Дульцев, Л.Л. Капуллер. – М.: Медицина, 1994. – 239 с.

- Changes in the QoL of patients suffering from acute or chronic hemorrhoids, who received conservative treatment, within 1 month after presenting to a doctor.
- Changes in the QoL of patients suffering from acute or chronic hemorrhoids, who received combination treatment, within 1 month after presenting to a doctor.
- Changes in the QoL of patients suffering from acute or chronic hemorrhoids, who underwent minimally invasive interventions, within 1 month after presenting to a doctor.
- Changes in clinical manifestations in patients suffering from acute or chronic hemorrhoids, and their association with demographic and clinical parameters, as well as the chosen treatment strategies (surgical, minimally invasive, or conservative).
- Patient's compliance with recommendations of a doctor.

Design:

The EQUALISER program is a Russian, multicenter, observational program.

In Russia, the program is scheduled for 2018-2019. It is expected that 90 doctors will take part in the program in 60 cities of the Russian Federation. The planned number of patients is 900. Each participating doctor includes at least 10 patients and fills out an electronic case report form (CRF). All treatment is carried out in accordance with the instructions for medical use and routine clinical practice.

| | |
|------------------------------------|---------|
| First visit of the first patient | 02/2019 |
| Last visit of the last patient | 05/2019 |
| Completion of statistical analysis | 08/2019 |
| Preliminary report | 12/2019 |
| Final report | 03/2020 |

Methods:

During the program, at each visit the leading clinical symptoms of hemorrhoids will be assessed.

The quality of life assessment will be carried out using the validated questionnaire SF36 (in Russian) (**Appendix 2**)

Inclusion visit (V0)

Patients who meet the inclusion criteria will be included in the program, and for them the CRF will be completed.

Visit 1 (V1) Surgical intervention (if applicable).

Visit 2 (V2) in 5-7 days after surgical intervention or 5-7 days after the Inclusion Visit (V0), if intervention was not performed.

Visit 3 (V3) in 25-30 days after surgical intervention or 25-30 days after Inclusion Visit (V0), if intervention was not performed.

| Visit | Actions |
|-------|---|
| V0 | 
 • Signing the Informed Consent Form |

| | |
|----|--|
| | 
 • Checking of fulfilment of inclusion/non-inclusion criteria. • Obtaining the data: 
 - Disease duration - Clinical manifestations of haemorrhoids - клинические проявления геморроя: 
 • prolapse of hemorrhoids (Appendix 4) • pain, itching, dyscomfort (Appendix 6) • bleeding - The Rome III criteria for constipation (Appendix 3) - Conservative treatment (systemic venotonic drug, topical agents, analgetics) - Diagnosis according to the National guidelines on coloproctology, 2015 (Appendix 5) - The surgical treatment scheduled - QoL assessment using the SF36 scale (Appendix 2) |
| V1 | 
 • Surgical treatment (if performed) |
| V2 | 
 • 5-7 days after intervention or after V0, if intervention was not performed • Clinical manifestations of haemorrhoids at the day of visit • Patient's compliance with doctor recommendations • Recording the adverse events (Appendix 1). • Assessment of pain, itching, and discomfort using VAS (Appendix 5) |
| V3 | 
 • 25-30 days after intervention or after V0, if intervention was not performed • Clinical manifestations of haemorrhoids at the day of visit • Patient's compliance with doctor recommendations • Patient's satisfaction with the treatment • Recording the adverse events • Clinical manifestations of haemorrhoids at the day of visit • QoL assessment using the SF36 scale |

Inclusion criteria

Patients fulfilment of the criteria of the inclusion in the program will be determined by the following parameters:

- 1) Age over 18 years;
- 2) Providing written information to a patient about inclusion in the program, and his/her consent to participate in it;
- 3) Absence of conditions requiring urgent medical care and not related to hemorrhoids;
- 4) The patient was diagnosed with:
 - Acute hemorrhoids (with thrombosis of hemorrhoids);
 - Exacerbation of chronic hemorrhoids (pain, bleeding, oedema (swelling) of hemorrhoids);
 - Chronic hemorrhoids (prolapsed hemorrhoids, bleeding events, anal discomfort).

Exclusion criteria

- 1) The patient is consulting for an urgent issue not related to hemorrhoids;
- 2) The presence of severe systemic diseases;
- 3) Pregnancy;

- 4) Inability to understand the meaning of the Program and follow the doctor's recommendations
- 5) Patients with inflammatory bowel diseases (Crohn's disease, non-specific ulcerative colitis);
- 6) Patients with concomitant diseases of the anal canal (fissure, fistulas, paraproctitis, etc.);
- 7) Patients taking anticoagulants;
- 8) Patients with previous anorectal surgeries, including hemorrhoidectomy or excision of anal fistula.

Treatment

The observational nature of program presumes that all examinations, procedures and changes in the treatment of patients, including changes in the dosing regimen, should be carried out only on the basis of judgment of the treating physician and in full compliance with the guidelines on the treatment of patients of the analysed population, instructions for medical use of drugs, and in the settings of daily routine practice.

Therapy is conducted in full accordance with existing guidelines. The patient's participation in the program, as well as his/her refusal to continue such participation, should not affect the current treatment, the availability of diagnostic procedures or the volume and quality of other necessary medical care.

Safety considerations

1. Definitions

1.1 Pharmacovigilance information

Pharmacovigilance data include any unintended or adverse event associated with the use of a medicinal product in humans, whether or not considered drug related, including the following special situations (situations where no adverse event occurred but information needs to be collected):

- exposure during pregnancy or breastfeeding;
- overdose, abuse, misuse, off-label uses, medication error, occupational exposure (including professional one);
- lack of the treatment efficacy of drug.

1.2. Adverse Event (AE)

Adverse event is any untoward medical occurrence in a patient or a clinical-trial subject who received the medicinal product, which does not necessarily have a causal relationship with the use of this medicinal product.

An adverse event can therefore be any unfavourable and unintended sign (e.g. an abnormal laboratory finding), symptom, or disease temporally associated with the use of a medicinal product, whether or not considered related to the medicinal product.

1.3. Adverse (drug) reaction (ADR)

Adverse reaction (synonyms: Adverse drug reaction, Suspected adverse (drug) reaction, Adverse effect, Undesirable effect) is a response to a medicinal product which is noxious and unintended.

“Response” in this context means that a causal relationship between a medicinal product and an adverse event is at least a reasonable possibility.

Adverse reactions may arise from use of the product within or outside the terms of the marketing authorization or from occupational exposure. Conditions of use outside the marketing authorization include off-label use, overdose, misuse, abuse and medication errors.

1.4. Serious adverse (drug) reaction (SADR)

Serious adverse reaction is an adverse reaction, which results in death, is life-threatening, requires in-patient hospitalisation or prolongation of existing hospitalisation, results in persistent or significant disability or incapacity, or is a congenital anomaly/birth defect.

“Life threatening” in this context refers to a reaction in which the patient was at risk of death at the time of the reaction; it does not refer to a reaction that hypothetically might have caused death if more severe.

Medical and scientific judgement should be exercised in deciding whether other situations should be considered serious reactions, such as important medical events that might not be immediately life threatening or result in death or hospitalisation but might jeopardise the patient or might require intervention to prevent one of the other outcomes listed above.

Examples of such events are intensive treatment in an emergency room or at home for allergic bronchospasm, blood dyscrasias or convulsions that do not result in hospitalisation or development of dependency or abuse.

Any suspected transmission via a medicinal product of an infectious agent is also considered a serious adverse reaction.

2. Responsibilities

2.1. Events to be reported

All available information about the following reported events occurring during the study will be recorded:

- All serious adverse drug reactions related to the use to Detralex
- All non-serious adverse drug reactions related to the use to Detralex
- All reports about special situations (see 1.1)
- All adverse events

2.2. Responsibilities of the investigator

In prospective studies, at medical visits, the investigator will ask the participating patient to indicate whether or not an adverse event (serious or not) has occurred.

The investigator has to assess the causal relationship between an adverse event and the investigated drug intake, as well as the seriousness criteria and later on the outcome of the event.

In case of Adverse Events, Adverse Drug Reactions or special situations that occurs during the study (both serious and non-serious), the investigator must complete the "Adverse event / Adverse drug reaction / Special Situation Reporting Form" (Appendix 1) without waiting for the clinical outcome or the results of additional investigations.

When assessing the quality of life using the EQ-5D, the investigator should evaluate data (patient's answers), their clinical relevance, and fill out the " Adverse event / Adverse drug reaction / Special Situation Reporting Form" if he/she considers these data as AE, ADR or a special situation.

If the event is serious, it will be notified immediately (same or next working day at the latest) to Servier company in Russia via e-mail to address [contact] or by fax to number [name]. The anonymized copies of all the available and relevant laboratory findings, hospitalisation reports or other investigation results performed in connection with the adverse event should be attached to the form.

All other events should be reported by investigator within 2 working days.

The same rules apply for the transferring of additional information about the event.

The investigator must ensure the appropriate follow-up of the patient depending on the nature of event, until it resolves.

The investigator will continue to notify follow up data according to timeframes defined above.

If investigator does not follow-up a patients anymore (i.e. in case of hospitalisation followed by the treatment by specialist or the participant's general practitioner,...), he/she will do every effort to contact the specialist or department in charge of follow-up of the patient, so as to have additional information and report it to Servier company in Russia.

2.3. Responsibilities of the Sponsor/Marketing Authorisation Holder

Independently of the regulatory obligations of investigator, the sponsor/MAH must report the pharmacovigilance data to the appropriate authorities in accordance with the Good Vigilance Practice and local regulations.

Cases are closed when an adverse event has recovered or patient's condition was stabilised and the report is deemed sufficiently detailed for adequate medical analysis of the case.

Ethical considerations

The study will be conducted in accordance with the principles set out in the Declaration of Helsinki (version adopted in Fortaleza, Brazil, in 2013).

The protocol of the program was reviewed and approved in accordance with the legislation of the Russian Federation and will be followed by the sponsor, in particular, with regard to data collection. Participants will be fully informed and provide their written consent to participate in the program. Investigator is obliged to indicate in the CRF that the informed consent was obtained from the patient, as well as to keep the signed Form in the clinical file for the participant. The "informed consent" also means that individual discussion with participant concerning the nature of the program and the necessary investigations. Sponsor will not have access to the data allowing identification of participants. Documents relating to the study will be reviewed by Ethical committee.

Organizational structure and responsibilities

Investigators

Investigators will receive informed consent forms and enroll participants, ensure data collection in accordance with the protocol, fill in case report forms and verify the accuracy of information in these case report forms, as much as possible. The patient will be provided with all information to obtain informed consent. At the same time, participants will be asked to consent to the use of their personal data. The data of the participants will remain completely confidential.

Sponsor

The sponsor will be responsible for all stages of the program, for providing the resources necessary to initiate and run the program in accordance with local regulations, as well as for the validity of the recorded data.

Statistical parameters

Variables:

- Change in the mean score of the EQ-5D index in patients suffering from acute or chronic hemorrhoids within 1 month after presenting a doctor, in general population and in specific demographic and clinical groups.
- Rates (in %) of different variables of health profile according to the EQ-5D in patients suffering from acute or chronic hemorrhoids, and their relationship to demographic, clinical parameters and the chosen treatment strategies (surgical, minimally invasive, and conservative).
- Change in the mean score of the EQ-5D index in patients suffering from acute or chronic hemorrhoids, who underwent surgical intervention, within 1 month after presenting to a doctor
- Change in the mean score of the EQ-5D index in patients suffering from acute or chronic hemorrhoids, who received conservative treatment, within 1 month after presenting to a doctor
- Change in the mean score of the EQ-5D index in patients suffering from acute or chronic hemorrhoids, who received combination treatment, within 1 month after presenting to a doctor
- Change in the mean score of the EQ-5D index in patients suffering from acute or chronic hemorrhoids, who underwent minimally invasive intervention, within 1 month after presenting to a doctor

- Change in the mean score by VAS (in mm) scale from SF36 questionnaire in patients suffering from acute or chronic hemorrhoids, who underwent surgical intervention, within 1 month after presenting a doctor, in general population and in specific demographic groups
- Change in the mean score by VAS (in mm) scale from SF36 questionnaire in patients suffering from acute or chronic hemorrhoids, who received conservative treatment, within 1 month after presenting to a doctor
- Change in the mean score by VAS (in mm) scale from SF36 questionnaire in patients suffering from acute or chronic hemorrhoids, who received combination treatment, within 1 month after presenting to a doctor
- Change in the mean score by VAS (in mm) scale from SF36 questionnaire in patients suffering from acute or chronic hemorrhoids, who underwent minimally invasive intervention, within 1 month after presenting to a doctor
- Change in the mean score by VAS (in mm) scale from CRF for pain, itching, and discomfort in patients suffering from acute or chronic hemorrhoids, within 1 month after presenting to a doctor, and their relationship to demographic, clinical parameters and the chosen treatment strategies (surgical, minimally invasive, and conservative).
- Change in the proportion (in %) of patients with bleeding events or prolapse of hemorrhoids among patients suffering from acute or chronic hemorrhoids, within 1 month after presenting a doctor, and its relationship to demographic, clinical parameters and the chosen treatment strategies (surgical, minimally invasive, and conservative).
- Proportion (%) of patients compliant with recommendations on lifestyle changes
- Proportion (%) of patients compliant with recommendations on medical therapy.

Statistical analysis:

Baseline characteristics will be analyzed in all included patients despite adherence to the protocol. Analysis of the results of program will be performed using the SPSS 12.0 software package (SPSS Inc., USA). The data entry errors will be corrected before the statistical processing. Quantitative parameters will be presented depending on the distribution of primary data as arithmetic mean \pm standard deviation for parametric variables, or as median (25; 75 percentiles) for nonparametric variables. Multiple comparisons will include adjustments for continuity.

Changes in the quantitative parameters during the follow-up period will be evaluated using the Student's t-test for paired samples or its nonparametric analogue, Wilcoxon test. Differences on the quantitative parameters, both between the independent groups and during the follow-up, will be evaluated as the mean difference with the corresponding 95% confidence interval.

Comparisons of changes on the VAS scales and the Rome III constipation scale will be carried out using two-factor analysis of variance (ANOVA) with repeated measures to compare the scores before and after the treatment.

Adverse events will be recorded and analyzed in patients with the reporting of all the AEs, SAEs, ADRs, SADRs and special situations.

Administrative considerations

The right to own the documentation, data and results of the program.

The sponsor reserves the exclusive rights for all materials, information, unpublished documentation, results and information received during the program. The sponsor reserves the right to send data on the program (case report forms, results of analyses, and reports) to health authorities.

No unpublished documentation or information transmitted to investigators can be transferred to unauthorized persons without the prior written consent of the Sponsor.

Publication and communication

Sponsor is responsible for communication and publication of data on the program. No aspect of the results of this program or other data may be published, presented, or distributed without the explicit written permission of Sponsor. Participants of the program fully transfer to the Sponsor the authority for the first presentation, communication and publication of the results on behalf of all employees. No other communication or publication is permitted before this first publication. Any subsequent communication or publication must first be considered and approved by the Sponsor and must refer to the program and the first publication.

APPENDIX 1

Adverse event / Adverse drug reaction / Special Situation Reporting Form*

IC4-05682-058-RUS Please send this form immediately by [contact] or by email to [contact], or pass to the associate of the company.

| Year of birth or | Age | Gender | Height | Weight | Patient's ID: |
|---|---|--|---|--|----------------------|
| _____ | or _____ | M / F | _____ | _____ | _____ |
| Description of adverse event/reaction/special situation: | | | Date of event onset | Date of event termination (in case of recovery) | |
| Criteria of seriousness:  NO  YES (please, specify from stated below) | | | Outcome:  Recovered  Recovered with consequences (persistent structural or functional impairment)  Not yet recovered  No recovery  Death  Unknown | | |
| General disease(s) / Concomitant disease(s) (please indicate year when first diagnosed). | | | | | |
| Course adverse event/reaction/special situation (please enclose relevant findings, e.g. laboratory, hospital reports, histology, etc.): | | | | | |
| Causal relationship with intake of investigational drug:    YES  NOT APPLICABLE | | | | | |
| If «Yes», please indicate dates of the use of investigational drug in the first line of the table below: | | | | | |
| If «No» or «Not applicable», please specify whether the adverse event/special situation is related to the medication of Servier company (which is specified in the table below): | | | | | |
|  NO  YES Please indicate the name of the medication of Servier company: | | | | | |
| List of current medications | Daily dose / route of administration | Dates of intake: from _____ to _____ | | Indication | |
| | | - | | | |
| | | | | | |
| | | - | | | |
| | | - | | | |
| | | | | | |
| Name (last, first, patronymic) of doctor: Speciality: Work address: Phone number: _____ (city code) | | | Date: Stamp (whenever possible) Signature: | | |

**Special situations are cases when adverse event was not observed, but the information should be collected: the impact of the drug during pregnancy/breastfeeding, abuse, misuse, medication error, overdose, off-label use, occupational exposure, or treatment failure...*

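### The bleeding/prolapse variable is the change in the overall proportion, so comparisons between strategies mix how common the symptom was at V0 with how often it resolved

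*Combined protocol and SAP*

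**What the plan says.** Under Statistical parameters, Variables, the protocol lists "Change in the proportion (in %) of patients with bleeding events or prolapse of hemorrhoids among patients suffering from acute or chronic hemorrhoids", measured over one month, together with "its relationship to demographic, clinical parameters and the chosen treatment strategies (surgical, minimally invasive, and conservative". This serves the secondary endpoint "Changes in clinical manifestations in patients suffering from acute or chronic hemorrhoids, and their association with demographic and clinical parameters". Nothing limits the denominator to patients who had the symptom at V0. Neither resolution nor new onset is defined, and the text does not say whether bleeding and prolapse are two outcomes or one.

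Inclusion criterion 4 does not require either symptom. It admits "Acute hemorrhoids (with thrombosis of hemorrhoids"), and for chronic disease it lists "Chronic hemorrhoids (prolapsed hemorrhoids, bleeding events, anal discomfort"), so discomfort stands beside the other two manifestations.

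On how strategy relates to grade, the Introduction says "The main method of treating chronic hemorrhoids of grade III-IV is surgical one" and that "the symptoms of hemorrhoids in grade 1-2 are successfully relieved with conservative treatment". Appendix 4 defines the grades largely by the degree of prolapse. The Treatment section leaves the choice of treatment to the physician.

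The Statistical analysis section names paired tests and mean differences for quantitative parameters, and repeated-measures ANOVA for the VAS and Rome III scales. It names no method for a change in a yes/no outcome and no adjustment for V0 status.

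**The concern.** A group cannot lose more of a symptom than it had at the start. If strategy A begins with most patients affected and strategy B with few, A can show the larger fall in percentage points even when the same share of affected patients recovers in both. A net change also offsets new onsets against resolutions, so neither can be read from it alone.

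Strategy here is chosen by the physician and, by the Introduction's own account, follows grade. Nothing in the design balances V0 prevalence across strategies, and nothing in the analysis separates it from resolution. What is at stake is the ranking of strategies on a secondary endpoint: a reader would take a larger fall as better symptom control, when it may only show that more patients had the symptom at entry.

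**Working it through.** The documents state no rate, effect size or power for this variable, so there is no planned figure to reproduce. All values of p0, r and q below are assumptions; the formula is an identity.

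**Formula.** Prevalence at V3 is p0·(1 − r) + (1 − p0)·q, so

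fall = p0 − V3 prevalence = p0·r − (1 − p0)·q.

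**Equal resolution (r = 70%), different V0 prevalence**

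| p0 | fall, q = 0 | fall, q = 5% |
|---|---|---|
| 90% | 0.90 × 0.70 = 63.0 points | 63.0 − 0.10 × 5 = 62.5 |
| 60% | 0.60 × 0.70 = 42.0 | 42.0 − 0.40 × 5 = 40.0 |
| 30% | 0.30 × 0.70 = 21.0 | 21.0 − 0.70 × 5 = 17.5 |

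At 90% against 30% with no new onset, the gap between strategies is 63.0 − 21.0 = 42.0 points, although resolution is identical. Resolution computed among affected patients would read 70% against 70%.

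**Reversal.** Take p0 of 90% and 40% with r of 60% and 90% (q = 0). The falls are 0.90 × 0.60 = 54 points and 0.40 × 0.90 = 36 points. The strategy with the lower resolution shows the larger fall.

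**How much of a gap is due to V0 prevalence?** With q = 0, the difference between two strategies splits into mean(p0) × (r1 − r2), the resolution part, and mean(r) × (p01 − p02), the prevalence part. The prevalence share of the summed absolute parts is:

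| p0 | r | resolution part | prevalence part | prevalence share |
|---|---|---|---|---|
| 90 v 30 | 70 v 70 | 0.0 | 42.0 | 100% |
| 90 v 50 | 90 v 80 | 7.0 | 34.0 | 83% |
| 90 v 50 | 90 v 60 | 21.0 | 30.0 | 59% |
| 90 v 80 | 90 v 50 | 34.0 | 7.0 | 17% |
| 95 v 90 | 90 v 60 | 27.8 | 3.7 | 12% |

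Over an even grid of p0 and r from 30% to 95%, the prevalence part is the larger one in 49% of combinations. The difference in falls has the opposite sign to the difference in resolution in 21%. The grid makes no claim to be realistic; it shows only that neither result is a corner case and neither is the rule.

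**Would such a gap be noticed?** Assume the planned 900 split evenly over four groups, 225 each; the documents give no group sizes. With q = 0 the fall is simply the share of patients who had the symptom and lost it. At equal 70% resolution, a two-sided 5% test of two proportions would declare a difference with probability of about 99% for p0 of 90% against 60% (63% v 42%), and about 33% for 90% against 80% (63% v 56%).

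**The case against.** The strongest reply is that the size is unknown and could be small. That stands. The documents give no V0 prevalence or resolution rate by strategy, and the prevalence share above runs from 12% to 100%. Appendix 4 also describes prolapse with bleeding in grade II, and even grade I as prolapse within the anal canal. Depending on how prolapse is coded, many conservatively treated patients may count as affected. If bleeding and prolapse form one combined outcome, it may be common in every group.

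A second reply is that change could be read as relative change. With no new onset, relative change equals r and the gap vanishes. The wording does not settle this, although a change in a percentage is most naturally read in points. The relative reading fails once there is new onset: with q = 5% and r = 70%, the relative falls are 62.5/90 = 69.4% and 17.5/30 = 58.3%. A report that shows both the V0 and V3 proportions would help a careful reader, but it would not separate resolution from onset.

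Third, the plan relates the change to clinical parameters, which leaves room for stratification. It does, but no such analysis is specified.

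Fourth, resolution among affected patients is itself confounded by grade when the physician chooses treatment. This is correct, so the remedy needs adjustment as well as a new denominator.

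Finally, the overall change is a legitimate description of the whole cohort. That stands in full.

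**Conclusion.** The point holds as a weakness in the comparison between strategies. As written, the variable mixes V0 prevalence with resolution and new onset, no planned method separates them, and the order of strategies can be misleading or reversed. This rests on the identity and on the stated denominator, and not on any assumed rate. The illustrative sizes (63 v 21 points at equal resolution; 54 v 36 points in the reversal) rest on assumed values. The concern is best supported for prolapse, because strategy is linked to grade and grade largely to prolapse. For bleeding or a combined outcome it may be small.

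Four stronger readings are tempting, and the documents do not support them:

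- **That the comparisons mostly reflect V0 prevalence.** No prevalence by strategy is given, and the share varies widely.
- **That prolapse must be far more common in the surgical group.** The link between strategy and grade makes an imbalance likely, but Appendix 4 places prolapse in the lower grades too.
- **That the V0 and V3 proportions will rest on different patients.** The sentence about analysing all included patients concerns baseline characteristics; for this variable no analysis set is stated.
- **That the same fault affects "Change in the mean score by VAS (in mm) scale from CRF for pain, itching, and discomfort".** The share of patients scoring zero at V0 is not given, a repeated-measures ANOVA is planned for the VAS, and restricting to scores above zero would select on a noisy baseline.

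This is a secondary variable in an observational program. The change is worth making because it is cheap.

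**What to change.** Amend the variable and add a short analysis paragraph:

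1. Treat bleeding and prolapse as separate outcomes, and state how prolapse is coded from Appendix 4.
2. For each symptom, in patients with both V0 and V3, report by strategy (a) the proportion resolved at V3 among those with it at V0 and (b) the proportion with new onset among those without it at V0, each with a 95% CI.
3. Compare strategies within these subsets, adjusted for or stratified by V0 grade or diagnosis, for example by logistic regression. Interpret the result as an observational association. Where strategy and grade barely overlap, say that the adjusted comparison rests on few patients.
4. Keep the overall change in proportion, in percentage points, as a paired before/after description (McNemar test with a paired CI), and do not use it to compare strategies.

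Clinical manifestations are already recorded at V0, V2 and V3, so no new data are needed. The cost is revised wording and a few tables, with smaller denominators and somewhat wider intervals for each symptom.
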